1. AMENDMENTS FROM PREVIOUS VERSION(S)

- Specifies analyses of safety data (adverse events and laboratory tests) which includes the period from the start of treatment with the axitinib + MK-3475 combination (CD1).
- Clarified language regarding analysis sets for efficacy endpoints. Clarified that data from patients treated at the MTD in the dose escalation and dose expansion portions of the study will be pooled for the secondary safety and efficacy analyses.
- Removed supportive efficacy analysis.

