The three dosing intervals are associated with three different dose-escalation decisions. The under-dosing interval corresponds to a dose escalation (E), over-dosing corresponds to a dose de-escalation (D), and proper-dosing corresponds to remaining at the current dose (R). Given a dosing interval and a probability distribution, the unit probability mass (UPM) of that dosing interval is defined as the probability of a subject belonging to that dosing interval divided by the length of the dosing interval. The mTPI design calculates the UPMs for the

three dosing intervals, and the one with the largest UPM informs the corresponding dose-finding decision, which is the dose level to be used for future patients. For example, if the under-dosing interval has the largest UPM, the decision will be to escalate, and the next cohort of patients will be treated at the next higher dose level. Ji and collaborators have demonstrated that the decision based on UPM is optimal in that it minimizes a posterior expected loss (ie, minimizes the chance of making a wrong dosing decision)⁵.

The dose-finding component of the trial is completed when at least 10 evaluable patients have been treated at the highest dose with DLT rate < 0.33. It is estimated that approximately 20 DLT evaluable patients have been enrolled to reach 10-DLT evaluable patients at the estimated MTD.

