8.3.2. Analysis of Efficacy Endpoints

PFS, DR, and OS will be summarized using the Kaplan-Meier method and displayed graphically. The median event time and 2-sided 95% confidence interval (CI), calculated using the Brookmeyer-Crowley method, for the median will be provided for each endpoint.

Six-month and twelve-month progression-free survival (6m-PFS and 12m-PFS) will be summarized as a product limit estimator based on the Kaplan-Meier method to account for censored events, together with the corresponding 2-sided 95% CI. The 2-sided 95% CI for the $\log[-\log(6 \text{ and } 12\text{-month PFS probabilities})]$ will be calculated using normal approximation and then back transformed to give the CI for the 6 and 12-month PFS rates. Analysis results will be included in the table for the PFS analysis.

The ORR will be summarized along with the corresponding exact 2-sided 95% CI calculated using a method based on the F distribution. If a patient has not achieved an objective response, but remain stable for at least 12 weeks, then the best overall response for such a patient will be SD.

For TTR, descriptive statistics including the mean (95% CI), median, and range will be provided.

Tumor Response will be presented in the form of patient data listings that include, but are not limited to, lesion type (target/non-target), received (maximum) dose, overall tumor response at each visit, and best overall response. In addition, progression date, death date, date of first response and last tumor assessment date, dates of first dose and last dose will be listed, together with DR, PFS and OS.

Listings or/and tables (when applicable) will be sorted by treatment cohort.

Analysis Sets

- Response-evaluable population for Tumor Response, PFS and OS (dose expansion cohort including the patients from the Dose Escalation Phase of the study treated at the MTD).
- Patients with an overall objective response of CR or PR in the response-evaluable population for Duration of Tumor Response and Time to Response (dose expansion cohort including the patients from the Dose Escalation Phase of the study treated at the MTD).

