8.3.5. Analysis of Biomarker Endpoints

Translational and pharmacodynamic biomarkers will be summarized using the appropriate biomarker analysis set. Summaries of baseline and ratio to baseline values at post-treatment visits will be provided using N, mean, standard deviation, median, % CV (as appropriate) and minimum/maximum for circulating biomarkers serum and tumor RNA measurements for potential gene signature development. Summary statistics will be provided for baseline values of circulating markers including VEGF-A, VEGFR2, IL8 and T-cell receptors, and archival tumor and baseline *de novo* biospecimens markers such as PD-L1 for all biomarker evaluable patients. Post-baseline values will be summarized for biomarker evaluable patients in the dose expansion cohort, when available.

Correlations of biomarker results with measures of anti-tumor efficacy will be examined for dose escalation and expansion cohorts separately. Summary of level of biomarkers at baseline and/or ratio of values to baseline versus ORR category will be made by timepoint. Summary of PFS and DR will be provided for dose expansion cohort after stratification by a preset cutpoint of biomarker values at baseline and/or ratio of values to baseline by timepoint. Receiver Operating Characteristics (ROC) analysis may be conducted for significant test results ($p < 0.05$) in correlations of PFS and/or ORR with PD-L1 expression level. Receiver Operating Characteristics (ROC) analysis may also be performed if significant test results ($p < 0.05$) in correlations of ORR and/or PFS with tumor RNA measurements are observed.

Graphical display will be provided for level of biomarkers at baseline and/or ratio of values

to baseline at each timepoint. Box and Whisker plots will be produced for level of biomarkers at baseline and/or ratio of values to baseline versus ORR category by timepoint in dose escalation and expansion cohorts separately. Kaplan-Meier plots will be produced for PFS and DR after stratification by $<$ or \geq median levels of biomarkers at baseline and/or ratio of values to baseline at each timepoint in the dose expansion cohort.

All biomarker data will be listed.

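### Splitting the biomarker-efficacy analyses by phase, when the efficacy endpoints themselves are pooled at the MTD, gives up precision for baseline blood and archival-tumour markers

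*SAP*

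**What the plan says.** SAP 8.3.5 groups the biomarker-efficacy work by phase. Correlations between markers and anti-tumour efficacy "will be examined for dose escalation and expansion cohorts separately", and the box plots of marker level by ORR category follow the same split. For time-to-event outcomes only one phase is used: "Summary of PFS and DR will be provided for dose expansion cohort after stratification by a preset cutpoint of biomarker values". The Kaplan-Meier plots by marker level are likewise drawn for expansion only.

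The efficacy endpoints are grouped differently. SAP 1 records that, for patients given the MTD, the two parts of the study are combined: "dose escalation and dose expansion portions of the study will be pooled for the secondary safety and efficacy analyses". SAP 8.3.2 defines the set for tumour response, PFS and OS, and for DR and TTR among responders, as the "dose expansion cohort including the patients from the Dose Escalation Phase of the study treated at the MTD". SAP 8.3.3 pools secondary safety in the same way.

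On samples, SAP 6.4 and footnote 27 of the protocol's Schedule of Activities plan archival tumour from all patients, and protocol 7.3.2 plans blood from all enrolled patients. Baseline de novo metastatic biopsies are planned for the expansion cohort only (SAP 6.4; footnote 28). SAP 8.3.5 summarises post-baseline marker values for the expansion cohort.

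**The concern.** ORR, PFS and DR will be reported on one set of patients and related to biomarkers on another. For markers that every patient contributes before treatment, the SAP does not say why dose-finding patients at the same assigned dose count towards the outcome but not towards the main analysis of its association with the marker.

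Three things are at stake. Precision is lost on a secondary objective (SAP 2.2.2), for which the expansion cohort was partly sized (SAP 8.1.3). The biomarker-stratified PFS and DR groups will not add up to the headline PFS and DR sets. Finally, ROC analysis is made conditional on a p-value below 0.05, but with two by-phase tests the SAP does not say which one counts.

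**Working it through.** **Inputs**
- Expansion cohort: 40 (SAP 8.1.3). SAP 4.2 makes this a ceiling of response-evaluable patients.
- Dose-finding patients at the MTD, m: at least 10. "The dose-finding component of the trial is completed when at least 10 evaluable patients have been treated at the highest dose with DLT rate <" (SAP 8.1.1; the limit on that rate is 0.33).
- All dose-finding patients: about 20 DLT-evaluable (SAP 8.1.3), so m runs from 10 to 20 on the planned numbers.
- PD-L1 positive rate: 20% (SAP 8.1.3).

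**The plan's own figures.** Worst-case SE = 1/(2√n). For n = 40 this is 0.0791 and for n = 39 it is 0.0801, so 40 is the smallest n that meets the SAP's limit of 0.08. PD-L1 positives: 0.20 × 40 = 8. Total: 20 + 40 = 60. All reproduce.

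**Pooling at the MTD**, with n = 40 + m:

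| m | n | m/n | Worst-case SE | SE relative to n = 40 | PD-L1 positives if archival tissue is used (0.20 × n) |
|---|---|---|---|---|---|
| 0 | 40 | 0% | 0.0791 | 1 | 8 |
| 10 | 50 | 20.0% | 0.0707 | √(40/50) = 0.894 | 10 |
| 20 | 60 | 33.3% | 0.0645 | √(40/60) = 0.816 | 12 |

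For de novo markers m = 0, so the first row applies and pooling adds nothing.

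**Illustrative power.** The documents give no effect sizes, and they state 0.05 without saying whether it is one- or two-sided. I assume two-sided 0.05.
- Correlation r, Fisher z: power ≈ Φ(√(n−3) × ½ ln[(1+r)/(1−r)] − 1.96).
- PFS by median split, with events in an assumed 60% of patients (d = 0.6n): power ≈ Φ(½√d × |ln HR| − 1.96).

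| Assumed effect | n = 40 | n = 50 | n = 60 |
|---|---|---|---|
| r = 0.3 | 47% | 56% | 65% |
| r = 0.4 | 73% | 83% | 89% |
| r = 0.5 | 92% | 97% | 99% |
| PFS HR 0.5 | 40% | 48% | 55% |
| PFS HR 0.4 | 61% | 71% | 79% |

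A dose-finding correlation on its own, at r = 0.4, has about 20% power with 10 patients and 42% with 20. The by-phase group in 8.3.5 is the whole dose-escalation cohort, so 20 is nearer the planned size. That group may mix dose levels if DL-1 is opened (protocol 3.1.1.2).

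**Effect of stratifying by phase.** If the two phase-specific Fisher z values are combined with weights n − 3, the information is 37 + 7 = 44 for m = 10, against 37 for expansion alone. The standard error is then √(37/44) = 0.917 of the expansion-only value, about 8% smaller. For m = 20 it is √(37/54) = 0.828, about 17% smaller. Most of the gain remains.

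**The case against.** The strongest reply is that a different grouping for a different analysis is a choice. SAP 1 limits pooling to the secondary safety and efficacy analyses. SAP 8.3.5 states its own grouping explicitly for the correlations, the PFS and DR summaries and both kinds of plot. Expansion-only PFS and DR also matches protocol 9.4, which gives efficacy summaries for expansion and only best-response listings for dose finding. This stands. A reader might infer that 8.3.5 was overlooked when pooling was introduced, but the documents do not show that.

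A reader might also infer that a fifth of the data is wasted. That goes too far. Dose-finding patients are used for ORR, in their own group. Their baseline markers are summarised and all biomarker data are listed. They are left out only of the biomarker-stratified PFS and DR analyses. A fifth is also just the low end of the planned range.

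The phases are not identical. All dose-finding patients have the 7-day axitinib lead-in, against at least 8 in expansion (protocol 3.1). Protocol 3.1.1.2 rules out intrapatient dose escalation in dose finding, whereas 5.2.7.1 permits axitinib increases without restricting them by phase; those passages must be reconciled. These are possible reasons for caution, although the SAP gives neither. They do not defeat pooling: 8.3.2 already accepts it for the same outcomes, PFS and OS start at C1D1 for everyone (SAP 6.1), and stratifying by phase deals with differences between phases.

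Lastly, the work is exploratory, with candidates to be validated in later trials (protocol 9.5.1.5), and SAP 4.1 puts estimation ahead of testing. That is right, and it limits how much this matters.

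**Conclusion.** The point holds as an inefficiency of limited scope. For baseline blood and archival-tumour markers against ORR, PFS and DR, the by-phase plan forgoes a reduction in worst-case standard error of about 11% with 10 dose-finding patients at the MTD, rising to about 18% with 20, or somewhat less once phase is stratified. These figures assume 40 evaluable expansion patients with usable samples and that the added patients are response- and biomarker-evaluable.

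A rise in expected PD-L1 positives from 8 to 10, or to 12 at most, follows only if status is read from archival tissue. The documents do not say which tissue defines it. If it is the de novo biopsy, the gain is zero.

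Nothing here affects the DLT endpoint, the MTD or the headline efficacy estimates. It is a cheap improvement.

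**What to change.** Amend SAP 8.3.5 as follows:
- For baseline blood and archival-tumour markers against ORR, PFS and DR, make the pooled MTD set of 8.3.2 the main analysis set, stratified by phase.
- Exclude patients treated at other dose levels from that set.
- Keep the by-phase correlations and box plots as supportive displays.
- Keep de novo and post-baseline markers to the expansion cohort, and say why.
- State which tissue defines PD-L1 status, and that the p-value condition for ROC analysis refers to the main set.

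If the separation was deliberate, give the reason instead.

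The cost is SAP wording and programming, with no new samples or visits. The downside is that the pooled set combines phases that differ in lead-in exposure and possibly in axitinib dose increases. Stratification by phase addresses this, and the conflict between protocol 3.1.1.2 and 5.2.7.1 should be resolved so that the difference can be described.

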4. HYPOTHESES AND DECISION RULES

4.1. Statistical Hypotheses

The emphasis of the final analyses will be on estimation of key summary statistics rather than hypothesis testing.

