8.1.3. Sample Size Determination

The sample sizes planned for the study arise from logistic feasibility and past experience with Phase 1b studies in oncology and are not entirely driven by statistical considerations. It is expected that approximately 60 patients will be required to achieve all study objectives.

Due to the dynamic nature of the Bayesian allocation procedure, the sample size of the Up-and-Down design using the mTPI approach cannot be determined in advance. It is estimated 20 DLT evaluable patients will be enrolled in the dose finding stage in order to have a reliable and accurate estimate of the MTD. In addition, there will be a Dose Expansion Phase cohort to characterize safety, biomarkers, and efficacy in terms of probability (p) of achieving an event of interest including, but not limited to, objective response (OR). The goal will be to estimate proportions of such patients with the standard error (SE) of not greater than 0.08, ie, by definition,

$$SE = \sqrt{\frac{p(1-p)}{n}} \leq \frac{1}{2\sqrt{n}}$$

Therefore, a sample of forty patients ($n=40$) in the Dose Expansion Phase cohort will allow estimation of the probability of achieving an event of interest with the standard error ≤ 0.08 .

The sample size estimate for the expansion cohort also takes into consideration the key tumor biomarker PD-L1 endpoints. If the observed rate of PD-L1 positives is 20% then approximately 40 patients would be required to enroll 8 PD-L1 positive patients.

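### Optional ROC analyses of PD-L1 and tumor RNA are conditional on p<0.05 in the same cohort, so any AUC reported is biased upward (low severity)

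*SAP*

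**What the plan says.** SAP 8.3.5 allows a ROC analysis for two kinds of marker, each under a significance condition. For PD-L1 it says that "Receiver Operating Characteristics (ROC) analysis may be conducted for significant test results", and the trigger is "significant test results ($p < 0.05$) in correlations of PFS and/or ORR with PD-L1 expression level". For RNA, ROC may also follow if "significant test results ($p < 0.05$) in correlations of ORR and/or PFS with tumor RNA measurements are observed". The verb is permissive in both places.

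The same section sets the analysis sample: "Correlations of biomarker results with measures of anti-tumor efficacy will be examined for dose escalation and expansion cohorts separately". SAP 8.1.3 gives the sizes: "a sample of forty patients ($n=40$) in the Dose Expansion Phase cohort", and for dose finding, "It is estimated 20 DLT evaluable patients will be enrolled in the dose finding stage". It also uses PD-L1 to support the expansion size: "If the observed rate of PD-L1 positives is 20% then approximately 40 patients would be required to enroll 8 PD-L1 positive patients".

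SAP 8.3.5 does not name the test behind the p-value, the number of RNA measurements, a multiplicity adjustment, a hold-out sample or an optimism correction. It plans no ROC for a marker that misses the threshold. SAP 4.1 says that the final analyses emphasize "estimation of key summary statistics rather than hypothesis testing". Protocol 9.5.1.5 describes the biomarker work as exploratory, lists regression, t-tests and ANOVA among the methods, and leaves validation of candidate markers to later trials.

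**The concern.** An AUC that is calculated only after a significant test on the same patients is drawn from the upper tail of its sampling distribution. With about 40 patients, the smallest AUC that can reach p<0.05 is already close to 0.7, so every marker that passes looks moderately discriminating, including one with no relation to response.

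Two uses are at stake. SAP 2.1 hopes that the translational work may ultimately inform a patient selection strategy, and an inflated AUC could mislead the choice of markers and the sizing of a validation study. Also, PD-L1 is the biomarker that helps to justify the expansion size, yet whether its AUC is produced depends on the result. A non-significant PD-L1 with a wide interval would be informative, but the plan provides no AUC for it.

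**Working it through.** **1. The plan's own figures.** The worst-case standard error of a proportion at n = 40 is 1/(2√40) = 0.0791, which meets the stated limit of 0.08. PD-L1 positives: 0.20 × 40 = 8. Both reproduce. The documents give no AUC, power or error rate for the ROC step.

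**2. Inputs.** Threshold p<0.05 (SAP 8.3.5), taken as two-sided. Cohort sizes 40 and about 20 (SAP 8.1.3). The documents assume no response rate for the combination, so 20% to 70% is an assumption. Within it, 32% is the first-line ORR for axitinib alone in Protocol 1.2.2.2.

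**3. Smallest AUC that can pass.** With m responders, k non-responders and n = m + k, the rank AUC of an unrelated continuous marker has mean 0.5 and SE = √[(n+1)/(12mk)]. It passes when it lies at least 1.96 SE from 0.5.

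**4. Mean AUC given a pass.** For a standard normal Z, the mean of |Z| given |Z|>1.96 is 2φ(1.96)/0.05 = 2 × 0.05845/0.05 = 2.338. The mean passing AUC, oriented to exceed 0.5, is therefore about 0.5 + 2.338 × SE. For a 20/20 split, SE = √(41/4800) = 0.0924. The limit is 0.5 + 1.96 × 0.0924 = 0.681, and the mean is 0.5 + 2.338 × 0.0924 = 0.716.

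The last two columns come from a simulation of 100,000 unrelated markers per row (continuity-corrected Wilcoxon test).

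| Assumed ORR, n = 40 | m / k | SE | Limit | Mean given pass, formula | Mean given pass, simulated | Share passing |
|---|---|---|---|---|---|---|
| 20% | 8 / 32 | 0.1155 | 0.726 | 0.770 | 0.767 | 4.7% |
| 32% | 13 / 27 | 0.0987 | 0.693 | 0.731 | 0.729 | 4.9% |
| 50% | 20 / 20 | 0.0924 | 0.681 | 0.716 | 0.714 | 4.9% |
| 60% | 24 / 16 | 0.0943 | 0.685 | 0.721 | 0.720 | 4.7% |
| 70% | 28 / 12 | 0.1008 | 0.698 | 0.736 | 0.734 | 4.9% |

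Without the condition, the simulated mean AUC is 0.50, or 0.57 to 0.59 if the direction is always chosen to favor the marker. A t-test in place of the Wilcoxon test gives 0.71 to 0.73 at 13, 20 and 28 responders.

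**5. Other sample sizes, ORR 20% to 70%.** Dose-finding cohort alone, n = 20: 0.81 to 0.88. If missing tissue leaves n = 30: 0.75 to 0.81. If patients from both phases were combined to n = 50: 0.69 to 0.74.

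**6. PD-L1 as a binary marker.** Take 8 of 40 positive and a 20/20 split, with x of the 8 positives being responders. The AUC is ½[x/20 + 1 − (8−x)/20]. Fisher's test passes only at x = 7 or 8, or the mirror values 1 or 0. The AUC is 0.65 at x = 7 and 0.70 at x = 8, with probabilities 0.0202 and 0.0016 in that tail. The mean given a pass is (0.0202 × 0.65 + 0.0016 × 0.70)/0.0218 = 0.654. With 13 or 28 responders it is 0.66.

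**7. How many unrelated RNA markers pass.** About 5 per 100 per endpoint. If K markers are independent, the chance of at least one pass is 1 − 0.95^K: 34% for K = 8 and 64% for K = 20. These counts are assumptions, because the SAP gives none.

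**8. Which corrections work.** For an unrelated marker at 20/20, bootstrap optimism correction applied after selection moves the mean passing AUC only from 0.717 to 0.712. A stricter threshold raises it: about 0.78 at p<0.005.

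**9. PFS.** No AUC can be computed, because the SAP does not say how a censored time becomes a binary or time-dependent ROC outcome.

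**The case against.** The strongest reply is that this is optional, hypothesis-generating work. The SAP promises no AUC, no decision in this trial depends on one, and Protocol 9.5.1.5 says that candidates will be validated elsewhere. All of that stands and keeps the severity low. It does not correct an AUC that is reported from this trial, and the discretion in the wording removes no bias.

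Three stronger readings are tempting, and the documents do not support them.

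- A reader might infer that a non-significant PD-L1 leaves no trace. In fact SAP 8.3.5 plans, whatever the p-value, biomarker summaries and box plots by ORR category, PFS and DR summaries by cutpoint, Kaplan-Meier plots split at the median, and full listings. Only the AUC is not planned.
- A reader might infer that the p<0.05 condition contradicts SAP 4.1. That section speaks of emphasis and does not exclude tests, and the protocol openly lists tests for biomarkers. The condition sits awkwardly with the emphasis, no more.
- A reader might infer that an AUC near 0.7 is what any unrelated marker will show. The figure applies only to markers that pass, about 5% of unrelated continuous ones per test, and it varies with cohort size, response rate and whether PD-L1 is dichotomized.

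It is also fair to say that the lack of adjustment and the reuse of the same patients are read from the SAP's silence. Whether an exploratory RNA screen in about 40 patients needs false discovery rate control is debatable, and this point does not rest on it.

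**Conclusion.** The point holds at low severity. As written, any AUC for PD-L1 or tumor RNA is conditional on significance in the data that produce it, and is biased upward. The sizes worked out above apply to markers unrelated to ORR. They rest on the assumed response rates, a two-sided test and the use of the same cohort for test and AUC. A marker with a real association would also be overstated, less so as power rises. The condition covers PD-L1 and tumor RNA only, not the circulating markers.

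**What to change.** **PD-L1.** Remove the p<0.05 condition. State that the AUC of PD-L1 expression for ORR in the expansion cohort will be reported with a 95% CI whatever the p-value.

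**Tumor RNA.** Report how many markers were tested. For any marker picked by its p-value, either label the AUC as apparent and uncorrected for selection, or give a cross-validated or bootstrap AUC in which the selection step is repeated inside each resample. False discovery rate control alone is not a remedy, because it is still a significance threshold. Nor is an optimism correction applied after selection (step 8).

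**PFS.** If a ROC analysis for PFS is still wanted, the SAP must first say how the outcome is defined.

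**Cost.** SAP wording and a little code, with no new data or patients. The PD-L1 interval may be wide and unimpressive: for a 20/20 split with no association, the half-width is about 1.96 × 0.0924 = 0.18. Corrected RNA AUCs will be lower than apparent ones.
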